1.0 TRIAL SUMMARY

Abbreviated Title	Stereotactic Body Radiation Therapy and In Situ Oncolytic Virus Therapy in Metastatic Triple Negative Breast Cancer and Metastatic Non-Small Cell Lung Cancer Followed by Pembrolizumab
Trial Phase	II
Clinical Indication	Metastatic triple negative breast cancer (TNBC) and metastatic non-small cell lung cancer (NSCLC)
Trial Type	Window of opportunity
Type of control	None
Route of administration	Pembrolizumab, intravenous infusion; oncolytic virus therapy (adenovirus-mediated expression of herpes simplex virus thymidine kinase [ADV/HSV-tk], intratumoral injection; valacyclovir, oral
Trial Blinding	None
Treatment Groups	1
Number of trial subjects	57 (TNBC, 28; NSCLC, 29)
Estimated enrollment period	18–24 months
Estimated duration of trial	36 months
Duration of Participation	Continuing until disease progression, unacceptable toxicity, or up to 24 months in subjects without disease progression
Estimated average length of treatment per patient	Continuing until disease progression, unacceptable toxicity, or up to 24 months in subjects without disease progression

[figure not shown]
2.0 TRIAL DESIGN

2.1 Trial Design

This is a Phase II window of opportunity study evaluating the efficacy and toxicity of stereotactic body radiation (SBRT) and in situ oncolytic virus therapy (adenovirus-mediated expression of herpes simplex virus thymidine kinase [ADV/HSV-tk]) followed by pembrolizumab in patients with metastatic triple negative breast cancer (TNBC) and metastatic non-small cell lung cancer (NSCLC).

2.2 Trial Diagram

vp = viral particle; t.i.d. = three times daily; IV = intravenously; Q3W = every 3 weeks.

3.0 OBJECTIVES

3.1 Primary Objective

Objective: To determine the objective response rate (ORR) of ADV/HSV-tk plus (+) valacyclovir therapy in combination with SBRT used as a window of opportunity treatment before pembrolizumab in patients with metastatic TNBC and metastatic NSCLC. Response Evaluation Criteria in Solid Tumors (RECIST) 1.1 will be used to assess treatment response. Modified immune-related response criteria (irRC; derived from RECIST 1.1) will also be documented.

3.2 Secondary Objectives

Objectives:

(1) To determine the duration of response (DoR) of ADV/HSV-tk + valacyclovir therapy in combination with SBRT used as a window of opportunity treatment before pembrolizumab in patients with metastatic TNBC and metastatic NSCLC.

- (2) To determine the overall survival (OS) rate of ADV/HSV-tk + valacyclovir therapy in combination with SBRT used as a window of opportunity treatment before pembrolizumab in patients with metastatic TNBC and metastatic NSCLC.
- (3) To determine the progression-free survival (PFS) rate of ADV/HSV-tk + valacyclovir therapy in combination with SBRT used as a window of opportunity treatment before pembrolizumab in patients with metastatic TNBC and metastatic NSCLC.
- (4) To document the toxicities associated with ADV/HSV-tk + valacyclovir therapy in combination with SBRT used as a window of opportunity treatment before pembrolizumab in patients with metastatic TNBC and metastatic NSCLC. Toxicity will be defined as any treatment-related death or any \geq Grade 3 hematological toxicity excluding alopecia and constitutional symptoms, as assessed by the National Cancer Institute Common Terminology Criteria for Adverse Events (NCI CTCAE) v4.03.
- (5) To document the antitumor activity of ADV/HSV-tk + valacyclovir therapy in combination with SBRT used as a window of opportunity treatment before pembrolizumab in patients with metastatic TNBC and metastatic NSCLC, as assessed by the RECIST 1.1. Modified irRC will also be documented.
- (6) To estimate the clinical benefit rate (CBR) of ADV/HSV-tk + valacyclovir therapy in combination with SBRT used as a window of opportunity treatment before pembrolizumab in patients with metastatic TNBC and metastatic NSCLC.

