4.1.1.4.5 Summary of Adverse Event Data⁶³

In the pembrolizumab monotherapy trials (KEYNOTE-001, KEYNOTE-002, KEYNOTE-012, KEYNOTE-013, KEYNOTE-28, and KEYNOTE-011 [monotherapy arm]), the overall incidence of AEs ranged from 83.0% (73 of 88 subjects in KEYNOTE-012) to 100% (10 of 10 subjects in KEYNOTE-011). The most commonly reported AEs included fatigue, diarrhea, decreased appetite, nausea, and anemia. The incidence of DRAEs ranged from 39.8% (35 of

88 subjects in KEYNOTE-013) to 80.0% (8 of 10 subjects in KEYNOTE-011). The most commonly reported DRAEs across all studies were nausea, fatigue, and diarrhea. The incidence of Grade 3–5 DRAEs across studies ranged from 6.8% (6 of 88 in KEYNOTE-013) to 12.0% (187 of 1562 subjects in KEYNOTE-001/002). The most commonly reported Grade 3–5 DRAEs were anemia, ALT increased, and AST increased. Most subjects who experienced an AE continued in the study, with the incidence of AEs leading to discontinuation ranging from 1.9% (8 of 430 subjects in KEYNOTE-28) to 12.3% (192 of 1562 subjects in KEYNOTE-001/002). The majority of AEs leading to discontinuation were not considered drug related. Discontinuations due to a DRAE were infrequent and ranged from 0% (no subjects in KEYNOTE-011) to 4.5% (4 of 88 subjects in KEYNOTE-013). The most commonly reported DRAEs leading to discontinuation were pneumonitis, ALT increased, and AST increased. The overall pattern of AEs observed in melanoma subjects enrolled in KEYNOTE-002 demonstrates the favorable safety profile of pembrolizumab compared with chemotherapy. Consistent with prior observations from randomized comparisons of the 2 mg/kg and 10 mg/kg dose levels when given Q3W, there are no important differences in the safety profile of pembrolizumab at these 2 dose levels, and both doses appear to have a favorable safety profile compared with chemotherapy.

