In the combination therapy trials KEYNOTE-021 and KEYNOTE-023, the overall incidence of AEs was 95.4% (62 of 65 subjects) and 80% (8 of 10 subjects), respectively. In KEYNOTE-021, the most commonly reported AEs across the dose regimens were fatigue (49.2%), constipation and nausea (26.2% each), decreased appetite (23.1%), diarrhea (18.5%), and anemia and alopecia (15.4% each). In KEYNOTE-023, the most commonly reported AEs across the dose regimens were neutropenia and thrombocytopenia (50.0% each), followed by anemia, respiratory tract infection, and back pain (30.0% each). The incidence of DRAEs was 86.2% (56 of 65 subjects) in KEYNOTE-021 and 60.0% (6 of 10 subjects) in KEYNOTE-023. In KEYNOTE-021, the most commonly reported DRAEs across the dose regimens were fatigue (35.4%); nausea, decreased appetite, and alopecia (13.8% each); diarrhea (12.3%); and constipation and AST increased (10.8% each). In KEYNOTE-023, the most commonly reported DRAEs across the dose regimens were neutropenia and thrombocytopenia (50.0% each); anemia (30.0%); and dysphonia, hiccups, and pruritis (20.0% each).

Grade 3–5 DRAEs were reported in 23.1% (15 of 65 subjects) in KEYNOTE-021 and 50.0% (5 of 10 subjects) in KEYNOTE-023. In KEYNOTE-021, the most common Grade 3–5 DRAEs across dose regimens were AST increased (6.2%) and anemia and ALT increased (4.6% each). In KEYNOTE-023, the only Grade 3–5 DRAEs that occurred in more than 1 subject across dose regimens were neutropenia (40.0%) and anemia (20.0%).

In KEYNOTE-021, most subjects continued treatment despite AEs, and only 4.6% of subjects discontinued study treatment due to an AE. Only 3.1% of subjects discontinued study treatment due to an AE that was considered related to the study treatment by investigators. AEs resulting in discontinuation were reported in 3.1% of subjects (2 of 65 subjects). Interstitial lung disease, dermatitis allergic, and drug eruption were the only AEs resulting in discontinuation and were reported in 1 subject each (1.5%). In KEYNOTE-023, no subjects discontinued study treatment due to an AE.

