5.6 Subject Withdrawal/Discontinuation Criteria

Subjects may withdraw consent at any time for any reason or be dropped from the trial at the discretion of the investigator should any untoward effect occur. In addition, a subject may be withdrawn by the investigator or Sponsor if enrollment into the trial is inappropriate, the trial plan is violated, or for administrative and/or other safety reasons. Specific details regarding discontinuation or withdrawal are provided in Section 7.1.4 – Other Procedures.

A subject must be discontinued from the trial for any of the following reasons:

- The subject or legal representative (such as a parent or legal guardian) withdraws consent.
- Confirmed radiographic disease progression
- Dose interruption that exceeds 21 days
- Unacceptable adverse experiences
- Any Grade 4 or greater AE
- Severe (Grade 3) or life-threatening (Grade 4) immune-mediated complication
- Intercurrent illness that prevents further administration of treatment
- Investigator's decision to withdraw the subject
- The subject has a confirmed positive serum pregnancy test
- Noncompliance with trial treatment or procedure requirements
- The subject is lost to follow-up
- Death
- Administrative reasons
- Discontinuation of pembrolizumab treatment may be considered for subjects who have attained a confirmed CR and have been treated for at least 8 cycles (at least 24 weeks) of pembrolizumab and have received at least 2 cycles of pembrolizumab beyond the date when the initial CR was declared. These subjects may be eligible for second course treatment as described in Section 5.2.3.
- Completion of 24 months (35 cycles) of pembrolizumab

NOTE: Subjects who stop pembrolizumab after completion of 24 months (35 cycles) may be eligible for retreatment if they progress after stopping pembrolizumab provided they meet the requirements detailed in Section 5.2.3. Subjects may be retreated in the Second Course Phase (Retreatment) for up to an additional 12 months (17 cycles [calculated starting with the first dose]).

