7.1.2.1 Adverse Event Monitoring

The investigator or qualified designee will assess each subject to evaluate for potential new or worsening AEs as specified in the Trial Flow Chart and more frequently if clinically indicated. Adverse experiences will be graded and recorded throughout the study and during the follow-up period according to the NCI CTCAE v4.03 (see Section 12.2). Toxicities will be characterized in terms of seriousness, causality, toxicity grading, and action taken with regard to trial treatment.

For both the TNBC and NSCLC cohorts, a safety run-in period will be implemented for the initial subjects enrolled onto the study. An initial cohort of 3 patients will be followed for toxicity through the first cycle of pembrolizumab. **The PI will submit a status update for the first 3 patients after each individual is enrolled onto this trial via a Reportable Event application.**

Please refer to Section 7.2 for detailed information regarding the assessment and recording of AEs and Section 8.0 for detailed information regarding the run-in cohorts.

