8.0 STATISTICAL ANALYSIS PLAN

8.1 Statistical Analysis Plan Summary

Sample Size: For the TNBC cohort, the null and alternate hypotheses are 19% ORR⁷⁸ and 39% ORR, respectively. For the NSCLC cohort, the null and alternate hypotheses are 20% ORR⁷⁹ and 40% ORR, respectively. For the TNBC cohort, the target response rate is 39%. With a sample size of 28 patients, if the observed number of responders is 11 (39.3%); the 95% CI estimate will have a margin of error of 18.1 percentage points (i.e., 21.2% to 57.4%) based on the normal approximation. For the NSCLC cohort, the target response rate is 40%. With a sample size of 29 patients, if the observed number of responders is 12 (41.4%); the 95% CI estimate will have a margin of error of 17.9 percentage points (i.e., 23.5% to 59.3%) based on the normal approximation. For both the TNBC and NSCLC cohorts, we will implement a safety run-in period for the initial subjects enrolled onto the study. An initial cohort of 3 patients will be followed for toxicity through the first cycle of pembrolizumab. **The PI will submit a status update for the first 3 patients after each individual is enrolled onto this trial via a Reportable Event application.** If only 1 of 3 patients experience toxicity, then 3 more patients will be enrolled. If no more than 1 of 6 patients experience toxicity, then the trial will be fully opened. The staggering interval will be 5 weeks for the run-in cohort.

Statistical Analysis: DoR, OS rate, PFS rate, and CBR will be analyzed. Safety profiles will also be assessed through summaries of AEs, SAEs, AEs leading to treatment discontinuation, and treatment-related death. The safety analysis will report the frequency of all AEs and laboratory abnormalities as well as the frequency of dose interruptions and toxicity-related treatment discontinuation. Toxicity rates will be presented using the worst NCI CTCAE grade per patient.

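### The safety run-in counts patients with toxicity, but the only definition of that word contradicts itself and, read literally, omits nonfatal Grade 3-4 pneumonitis, colitis and hepatitis

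*Combined protocol and SAP*

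**What the plan says.** Section 3.2, secondary objective (4), defines toxicity, graded by CTCAE v4.03, as treatment-related death or any event at or above "Grade 3 hematological toxicity excluding alopecia and constitutional symptoms". No other definition of toxicity or of dose-limiting toxicity appears in the document. The term unacceptable toxicity, used in Sections 1.0, 5.2, 5.2.1.2 and 6.1, is not defined either.

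Section 8.1 sets a safety run-in for both cohorts. Three patients are followed through the first pembrolizumab cycle, and two decision rules follow: "If only 1 of 3 patients experience toxicity, then 3 more patients will be enrolled" and "If no more than 1 of 6 patients experience toxicity, then the trial will be fully opened". Section 8.1 neither defines toxicity for this purpose nor refers to Section 3.2(4). Section 7.1.2.1 describes the run-in briefly and sends the reader to "Section 8.0 for detailed information regarding the run-in cohorts", which adds no definition.

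Elsewhere the protocol gives weight to organ toxicity. Section 4.1.1.4.5 states: "The most commonly reported DRAEs leading to discontinuation were pneumonitis, ALT increased, and AST increased". It gives the most common Grade 3-5 drug-related events as "anemia, ALT increased, and AST increased". Section 5.6 lists, among the reasons a subject must be discontinued, "Severe (Grade 3) or life-threatening (Grade 4) immune-mediated complication". Table 3 holds or permanently stops pembrolizumab for Grade 3-4 colitis, pneumonitis and AST, ALT or bilirubin increases.

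**The concern.** Alopecia and constitutional symptoms are not hematological events. Excluding them from a hematological category has no effect, so either the category or the exclusion is wrong.

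The word decides something. The run-in is the only rule in the protocol that turns a count of affected patients into a decision on exposing more patients to intratumoral vector, SBRT and pembrolizumab together. If the definition is followed as written, the events most often behind drug-related discontinuation of pembrolizumab add nothing to the count unless they are fatal. If it is not followed, two competent readers can score the same six patients differently and reach opposite decisions.

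**Working it through.** **Step 1. Test each reading of the definition.**

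| Reading | What counts | What is lost |
|---|---|---|
| (a) Literal | Treatment-related death; Grade 3+ hematological events | All nonfatal Grade 3-4 non-hematological events, including pneumonitis, colitis, hepatitis and ALT or AST increases |
| (b) Slip for non-hematological | Treatment-related death; Grade 3+ non-hematological events other than the two exclusions | Nonfatal cytopenias, although anemia is among the most common Grade 3-5 drug-related events in Section 4.1.1.4.5 |
| (c) Section 3.2(4) does not govern the run-in | Nothing specified | The criterion itself |

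Under (a), none of the three leading drug-related causes of discontinuation counts when nonfatal. Of the three most common Grade 3-5 drug-related events, only anemia counts. In the extreme case, all six run-in patients could be discontinued under Section 5.6 for nonfatal Grade 3-4 immune-mediated events that are not hematological, and the run-in count would still be 0 of 6.

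**Step 2. How the rule behaves when events do count.** The plan states no operating characteristic for the run-in, so there is no figure to reproduce. Let *p* be the probability that a patient has a counted event. Section 8.1 does not say what happens at 0 of 3 or at 2-3 of 3, so two versions are shown.

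- Version A (assumed: 0 of 3 opens, 2 or more of 3 does not): P(open) = (1−p)³ + 3p(1−p)² × (1−p)³
- Version B (opening always needs at most 1 of 6): P(open) = (1−p)⁶ + 6p(1−p)⁵

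The first three rates are Grade 3-5 drug-related event rates from Section 4.1.1.4.5. The last two are assumed.

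| p | Source | Version A | Version B |
|---|---|---|---|
| 6.8% | 6/88, KEYNOTE-013 | 0.95 | 0.94 |
| 12.0% | 187/1562, KEYNOTE-001/002 | 0.87 | 0.84 |
| 23.1% | 15/65, KEYNOTE-021 | 0.64 | 0.58 |
| 30% | assumed | 0.49 | 0.42 |
| 40% | assumed | 0.31 | 0.23 |

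Worked example for version A at 12.0%: 0.88³ + 3 × 0.12 × 0.88⁵ = 0.681 + 0.190 = 0.87.

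**Step 3. The literal definition.** Under reading (a), *p* contains only treatment-related deaths and Grade 3+ hematological events. The rate *u* of nonfatal Grade 3-4 non-hematological events does not enter either formula, so P(open) is constant in *u*. To show the contrast, assume a literally counted rate of 5% and an independent *u*. If all Grade 3+ events counted, p = 1 − 0.95(1 − u).

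| u (assumed) | Literal, A (B) | All Grade 3+ counted, A (B) |
|---|---|---|
| 10% | 0.973 (0.967) | 0.824 (0.788) |
| 30% | 0.973 (0.967) | 0.425 (0.348) |
| 50% | 0.973 (0.967) | 0.145 (0.088) |

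**The case against.** **The link is not explicit.** The definition sits under a secondary objective about documenting toxicities, and Section 8.1 does not cite it. That is true, but it leads to reading (c), under which the run-in has no criterion. It replaces one defect with another.

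**The literal reading is unlikely to be intended.** The exclusion clause makes sense only if non-hematological events were in scope, and Table 3 and Section 5.6 show that such events matter to the authors. This also stands as a point about intent. But the protocol does not say what was meant, and simply substituting non-hematological drops cytopenias. A definition that has to be guessed cannot support a counting rule.

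**Other safeguards exist.** The run-in has a 5-week stagger and a mandatory status update for each of the first three patients. Section 5.2.1.2 requires vector de-escalation for unacceptable toxicity. Section 5.6 discontinues individual subjects. Section 5.7 allows early termination for a health hazard. Section 7.2.3 requires SAE reporting to the sponsor within 24 hours, and the sponsor monitors aggregate safety data. These events would therefore be seen. But each measure is per patient, concerns reporting or timing, or has no stated threshold; none counts patients to decide whether a cohort opens.

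**The numbers may overstate the effect.** This stands in part. The highest cited rate (events that "were reported in 23.1% (15 of 65 subjects) in KEYNOTE-021") is from a trial that combined pembrolizumab with chemotherapy, ipilimumab, erlotinib or gefitinib, and Section 4.1.1.4.5 itself rules out comparative evaluation from the small combination studies. At the two lower rates the cohort opens with probability 0.84 to 0.95 even if every event counts. For the three named conditions, the same section gives drug-related serious event rates in monotherapy of at most 1.3% (pneumonitis), 0.9% (colitis) and 0.7% (hepatitis). Summed without overlap these make 2.9%, and P(open) is then 0.991 (A) or 0.988 (B). Serious is not the same as Grade 3-4, and monotherapy rates need not carry over to this combination. A run-in is there for the case where the combination turns out worse than expected, and the literal count cannot detect that for these events.

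**Conclusion.** The concern holds, and the text must be corrected. The main finding needs no assumed rate: the only definition of toxicity is internally inconsistent, and under its literal reading the probability of opening a cohort is unaffected by nonfatal Grade 3-4 non-hematological events, however frequent. The other two readings also leave the run-in without a sound criterion.

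The P(open) values are illustrations. They rest on rates from other regimens over all follow-up, with hematological events included, or on assumed rates, and on branches that Section 8.1 does not state. They also take the run-in to apply separately to each cohort, which the text supports but does not spell out. The unstated actions at 0 of 3 and at 2-3 of 3 are missing detail and secondary to the faulty definition.

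**What to change.** Reconcile the definition in Section 3.2(4) with its own exclusion clause and with the organ toxicities that Section 5.6 and Table 3 treat as treatment-limiting. Which events count is for the clinical team to decide. Cite the reconciled definition in Section 8.1 as the run-in criterion, and state there what happens at 0 of 3 and at 2 or 3 of 3.

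The cost is a short text amendment to two sections. Depending on which events are included, the run-in may expand or pause more often and enrollment may slow. As a guide, if every Grade 3-5 drug-related event counted at a 12.0% rate, the chance that a cohort would not open under the rule would be about 1 − 0.87 = 0.13 (version A) or 1 − 0.84 = 0.16 (version B).

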3.3 Exploratory Objectives

Objectives:

- (1) To determine the abscopal effect of ADV/HSV-tk + valacyclovir therapy in combination with SBRT followed by pembrolizumab. The primary criterion for abscopal effect evaluation will be computed tomography (CT)-based response assessment (RECIST 1.1) of a non-target lesion. The secondary criterion will be immune parameters including programmed death-1 (PD-1) and programmed death-ligand 1 (PD-L1) expression, immune infiltrates, and cytokine expression (interleukin [IL]-1, IL-2, IL-6, IL-12, interferon [IFN]-c, tumor necrosis factor- α [TNF- α], and granulocyte macrophage colony-stimulating factor [GM-CSF]).
- (2) To measure the immune response to ADV/HSV-tk + valacyclovir therapy in combination with SBRT followed by pembrolizumab in patients with metastatic TNBC and metastatic NSCLC.
- (3) To explore correlative tissue and blood-based biomarkers including but not limited to T-cell cytokine profiles (IL-1, IL-2, IL-6, IL-12, [IFN-c, TNF- α , and GM-CSF), tumor-infiltrating lymphocytes (TILs), PD-1 and PD-L1 expression, effector and suppressor immunocyte populations, and mutation load.

4.0 BACKGROUND & RATIONALE

4.1 Background

Despite the significant advances in our understanding of breast cancer biology, limited progress has been made in the treatment of advanced breast cancer. There has been little change in the OS of women with treatment-resistant metastatic breast cancer over the last several decades.¹ Notably, approximately 40,000 women with metastatic breast cancer die each year primarily due to treatment resistance and failure. TNBC is a mutationally complex breast cancer subtype with poor prognosis and no current targeted therapy options. Compared with other intrinsic breast cancer subtypes, TNBC has higher expression levels of PD-L1 and its receptor PD-1, which may hinder antitumor T cell responses. Immunotherapy has demonstrated promising efficacy in pretreated metastatic TNBC and appears to be one of future treatment choices for resistant cancers.²

Lung cancer is the leading cause of cancer death in the United States. Lung cancer is expected to account for an estimated 224,390 new cases (117,920 in men and 106,470 in women) and 158,080 deaths (85,920 in men and 72,160 in women) in 2016.¹ Only 16.8% of lung cancer patients are alive for 5 years or more after their diagnosis. NSCLC accounts for over 85% of all lung cancer cases. Most patients are diagnosed with advanced or metastatic (stage IIIB/IV) disease,³ and current first-line treatment options for these patients are limited. In patients with advanced NSCLC, first-line platinum-based doublet chemotherapy yields 1-year OS rates of only 30–40% and can cause significant toxicities that may complicate treatment.³ However, much progress has recently been made in the diagnosis and treatment of lung cancer including screening methods, minimally invasive techniques for diagnosis and treatment, and advances in radiation therapy (RT) including SBRT, targeted therapies, and immunotherapies.⁴⁻⁸

Cancer immunotherapy harnesses and boosts the innate powers of the immune system to fight cancer and represents the most promising new cancer treatment approach since the development of chemotherapeutic agents in the late 1940s. Because of the extraordinary memory and specificity of the immune system, immunotherapy has the potential to achieve complete, long-lasting remissions with few or no side effects in cancer patients, regardless of their cancer type. Immunotherapies targeting PD-1 have shown unprecedented rates of durable clinical responses in patients with various cancer types.⁹⁻¹³ Upregulation of PD-L1 and its ligation to PD-1 on antigen-specific CD8⁺ T-cells (termed adaptive immune resistance) represents a major mechanism by which cancer tissues limit the host immune response.^{14, 15} Under healthy conditions, PD-1, expressed on the cell surface of activated T-cells, functions to downmodulate unwanted or excessive immune responses, including autoimmune reactions. PD-1 (encoded by the gene *Pdcd1*) is an immunoglobulin (Ig) superfamily member related to CD28 and cytotoxic T-lymphocyte-associated antigen-4 (CTLA-4) that has been shown to negatively regulate antigen receptor signaling upon engagement of its ligands (PD-L1 and/or PD-L2). The structure of murine PD-1 has been resolved. PD-1 and its family members are type I transmembrane glycoproteins containing an Ig variable-type (V-type) domain responsible for ligand binding and a cytoplasmic tail responsible for the binding of signaling molecules. The cytoplasmic tail of PD-1 contains two tyrosine-based signaling motifs, an

immunoreceptor tyrosine-based inhibition motif and immunoreceptor tyrosine-based switch motif (ITSM). Following T-cell stimulation, PD-1 recruits the tyrosine phosphatases Src homology phosphatase (SHP)-1 and SHP-2 to the ITSM motif within its cytoplasmic tail. This leads to the dephosphorylation of effector molecules such as CD3 ζ , protein kinase- θ , and ZAP70, which are involved in the CD3 T-cell signaling cascade. The mechanism by which PD-1 downmodulates T-cell responses is similar to but distinct from that of CTLA-4, as both molecules regulate an overlapping set of signaling proteins. PD-1 was shown to be expressed on activated lymphocytes including peripheral CD4⁺ and CD8⁺ T-cells, B-cells, regulatory T cells (Tregs), and natural killer (NK) cells. PD-1 expression has also been shown during thymic development on CD4-CD8⁻ (double negative) T-cells as well as subsets of macrophages and dendritic cells (DCs). The ligands for PD-1 (PD-L1 and PD-L2) are constitutively expressed or can be induced in a variety of cell types, including non-hematopoietic tissues and various tumors. Both ligands are type I transmembrane receptors containing both IgV- and Ig constant-like domains in the extracellular region and contain short cytoplasmic regions with no known signaling motifs. Binding of either PD-1 ligand to PD-1 inhibits T-cell activation triggered through the T-cell receptor. PD-L1 is expressed at low levels on various non-hematopoietic tissues, most notably on vascular endothelium, whereas PD-L2 protein is only detectably expressed on antigen-presenting cells found in lymphoid tissue and chronic inflammatory environments. PD-L2 is thought to control immune T-cell activation in lymphoid organs, whereas PD-L1 serves to dampen unwarranted T-cell function in peripheral tissues. Although healthy organs express little (if any) PD-L1, a variety of cancers have been demonstrated to express abundant levels of this T-cell inhibitor. PD-1 has been suggested to regulate tumor-specific T-cell expansion in subjects with melanoma. This suggests that the PD-1/PD-L1 pathway plays a critical role in tumor immune evasion and should be considered an attractive target for therapeutic intervention.

Clinical trials have demonstrated the therapeutic potential of PD-1 blockade therapy. Brahmer et al. demonstrated that, among patients with previously treated advanced squamous NSCLC, OS, response, and PFS rates were significantly better with the PD-1 inhibitor nivolumab than with docetaxel regardless of PD-L1 expression level. The confirmed ORR was significantly higher with nivolumab than with docetaxel (20% [95% confidence interval (CI): 14–28] vs. 9% [95% CI: 5–15]; $P = 0.008$).¹⁶ Herbst et al. found that treatment with MPDL3280A, a PD-L1-specific monoclonal antibody (mAb), induces therapeutic responses in patients with advanced NSCLC, renal cell cancer, and melanoma.¹⁷ Powles et al. showed that the same antibody can be used to treat urothelial bladder cancer. Among patients with a minimum of 6 weeks of follow-up, ORRs were 43% (13/30; 95% CI: 26–63) for those with tumor PD-L1 immunohistochemical (IHC) expression scores of 2 or 3 (2/3) and 11% (4/35; 95% CI: 4–26) for those with tumor PD-L1 IHC expression scores of 0 or 1 (0/1). In the tumor PD-L1 IHC expression 2/3 score group, the ORR included a 7% complete response (CR) rate (2/30). Among patients with a tumor PD-L1 IHC expression score of 2/3 and a minimum of 12 weeks of follow-up, an ORR of 52% (13/25; 95% CI: 32–70) was achieved. Sixteen of the 17 responders had ongoing responses, and all 17 responders continued on MPDL3280A treatment until the data cutoff. One patient who initially responded at the first response assessment later presented with new lesions, including a bladder mass thought to be consistent with pseudo-progression.¹⁸ Anti-PD-L1 immunotherapy has also shown promising results in TNBC.² The

latest data analysis of a Phase I clinical trial of MPDL3280A in TNBC revealed a 24-week PFS rate of 27% and ORR rate of 19%, with three of four responses ongoing. This data is encouraging, because longer responses do not typically occur in metastatic TNBC patients treated with chemotherapy, the standard of care for this population.² Together, these studies demonstrate the durable responses and low toxicity rates of anti-PD-1 immunotherapy. This is particularly important as high-grade adverse effects have limited the use of immunotherapy for cancer treatment in the past. PD-L1/PD-1 expression in cancer cells is an obvious candidate biomarker for immunotherapy response, as PD-L1/PD-1 can directly turn off the immune response by inhibiting the activity of tumor-infiltrating cytotoxic T-lymphocytes (CTLs). However, PD-L1 and PD-1 expression in tumor cells has been shown to have little predictive power. On the other hand, Herbst et al. reported that PD-L1 expression in immune cells is a good biomarker of response to immunotherapy.¹⁷ The finding that the complexity of the T-cell population in the tumor infiltrate can predict good response to checkpoint blockade therapy highlights the importance of identifying tumor antigens that can elicit an effective antitumor immune response. Previous studies have suggested that tumors with a high load of somatic mutations are more likely to respond to immunotherapy, as in theory these tumors would have a higher diversity of neoantigens that can trigger an immune response when CTLA-4/PD-1 inhibition is bypassed.

Pembrolizumab (MK-3475) is a potent and highly selective humanized mAb of the IgG4/kappa isotype designed to directly block the interaction between PD-1 and its ligands, PD-L1 and PD-L2. Antibody-mediated PD-1 blockade with pembrolizumab and other similar agents reinvigorates the immune system, allowing for cancer cell targeting and destruction. Pembrolizumab is one of a number of closely related therapies dubbed immune checkpoint blockade.¹⁹ On September 4, 2014, Keytruda™ (pembrolizumab) was approved by the United States Food and Drug Administration (FDA) for the treatment of patients with unresectable or metastatic melanoma and disease progression following ipilimumab and, if BRAF V600 mutation positive, a BRAF inhibitor. On October 2, 2015, Keytruda™ (pembrolizumab) received accelerated FDA approval for the treatment of patients with metastatic PD-L1-positive NSCLC whose disease has progressed on or after platinum-containing chemotherapy or targeted therapy against anaplastic lymphoma kinase (ALK) or epidermal growth factor receptor (EGFR), if appropriate. Keytruda™ is approved for use with a companion diagnostic, the PD-L1 IHC 22C3 pharmDx test, the first test designed to detect PD-L1 expression in NSCLC tumors. FDA approval for both disease indications was based on the results from the open label, first-in-human Phase Ib KEYNOTE-001 study (NCT01295827) of pembrolizumab in patients with progressive locally advanced or metastatic carcinomas. The melanoma cohort included patients with advanced disease previously treated with ipilimumab or ipilimumab in combination with a BRAF inhibitor (for *BRAF* mutation carriers).²⁰ After mandatory biopsy, patients were treated with one of three doses of pembrolizumab for 12 weeks; responders continued on treatment until disease progression. Among 173 patients treated with the recommended 2-mg/kg pembrolizumab dose, the overall response rate was 24%, with a DoR of 1.4 to 8.5 months. The NSCLC cohort included 550 patients with metastatic disease.²¹ The ORR in the efficacy population, which comprised 61 patients with PD-L1 strongly positive tumors, was 41% (95% CI: 28.6–54.3); all were partial responses (PRs). At the time of the analysis, responses were ongoing in 21 of 25 (85%) patients, with 11 (44%) patients having a

DoR of ≥ 6 months. The most commonly occurring ($\geq 20\%$) adverse events (AEs) included fatigue, decreased appetite, dyspnea, and cough. The most frequent ($\geq 2\%$) serious AEs (SAEs) were pleural effusion, pneumonia, dyspnea, pulmonary embolism, and pneumonitis. Immune-mediated AEs occurred in 13% of patients and included pneumonitis, colitis, hypophysitis, and thyroid disorders. Multiple ongoing clinical trials in all phases (NCT02551432, NCT02520154, NCT02530502, NCT02446457, NCT02306850, NCT02402920, NCT02298959, and NCT02560636) are evaluating pembrolizumab monotherapy and combination therapies for the treatment of all stages of liquid and solid malignancies, including TNBC. The KEYNOTE-086 study (NCT02447003) is a Phase II trial of pembrolizumab monotherapy in metastatic TNBC patients. The KEYNOTE-119 study (NCT02555657) is an open label, randomized Phase III study of single-agent pembrolizumab versus single-agent chemotherapy per physician's choice for metastatic TNBC. The KEYNOTE-173 study (NCT02622074) is a Phase Ib study to evaluate the safety and clinical activity of pembrolizumab in combination with chemotherapy as neoadjuvant treatment for TNBC. Together, these studies will pave the way for expanding the indications for pembrolizumab.

RT is proven to provide local tumor control. RT has traditionally been thought to mediate tumor regression through direct cytotoxic effects. However, it is now known that RT also alters the local tumor microenvironment to affect both local and systemic antitumor immune responses. There is growing evidence that the rational integration of RT with the expanding armamentarium of clinically approved immunotherapeutics can yield potent antitumor responses exceeding those of either therapy alone.²² The beneficial effects of RT in cancer patients extend beyond direct tumor cell cytotoxicity. Delivery of localized radiation to tumors often leads to systemic responses at distant sites, a phenomenon known as the abscopal effect, which has been attributed to the induction and enhancement of endogenous antitumor innate and adaptive immune responses. The mechanisms surrounding the abscopal effect are diverse and include trafficking of lymphocytes into the tumor microenvironment, enhanced tumor recognition and killing via upregulation of tumor antigens and antigen-presenting machinery, and induction of positive immunomodulatory pathways.²³ Cytokines play an important role in the abscopal effect. In one case, a Japanese patient receiving RT for thoracic vertebral bone metastasis experienced spontaneous regression of an unrelated hepatocellular carcinoma. Pre- and post-analyses of serum cytokine levels revealed a marked elevation in TNF- α following RT, suggesting that abscopal-mediated regression may involve such cytokines as part of the host immune response.²⁴ RT-induced IFN- β has been shown to enhance T-cell-dependent tumor regression by increasing the cross-priming capacity of tumor-infiltrating DCs *in vivo*. This effect can be mimicked by exogenous IFN- β delivery to tumor tissues.²⁵ Immune cell mediation of the abscopal effect is supported by the observation that exogenous administration of chemokines following local RT enhances tumor cell killing at distal sites. This abscopal effect was tumor-type independent and involved the infiltration of CD8⁺ and CD4⁺ lymphocytes and NK1.1⁺ NK cells into the tumor sites of mice.²⁶ The abscopal effect remains an active area of investigation in the immunotherapy field. CTLA-4, a negative regulator of cytotoxic CD8⁺ T-cells, has been targeted as a means to activate antitumor immune CTLs. CTLA-4 blockade has been shown to decrease the threshold of activation of endogenous tumor-reactive T-cells in mouse xenografts.²⁷ Local RT and CTLA-4 blockade have recently been shown to significantly reduce the motility of TILs at tumor sites, thereby allowing TILs

to engage in stable interactions with tumor targets.²⁸ The NK group 2, member D (NKG2D) ligand retinoic acid early inducible-1 is upregulated in irradiated neoplastic cells; interaction with its receptor, NKG2D, on CTLs costimulates and enhances tumor cell killing. T-cell receptor, NKG2D, and CTLA-4-transduced signals contribute to the stability of the immunological synapse. Their association appears to be mediated in part by increased antibody responses to the multiple tumor antigens released after RT.²⁹

Multiple factors contribute to the development of an abscopal effect. The abscopal effect involves the interplay of irradiation and induction of adaptive immune responses leading to tumor cell elimination at distant sites. Antitumor CTL responses, which represent the outcome of an abscopal effect primed by irradiated tumor cells, seem to play a significant role in RT-induced antigen-specific immunity.³⁰ Further evidence that antigen-specific T cells are elicited after RT is borne out by studies demonstrating a significant CD8+ T-cell-mediated reduction in systemic tumor burden after local ablative RT.³¹ T-cell priming following RT-mediated tumor cell death has been postulated to occur through DC cross presentation of released tumor antigens in draining lymph nodes, leading to primary or metastatic tumor rejection.

